3.4.2 Study Completion

The study is expected to reach its final completion 48 months from the time the study opens to accrual.

4 Study Drugs

4.1 Description, Supply and Storage of Investigational Drugs

4.1.1 Investigational Drug #1

Gallium-68 labeled PSMA-11 (or PSMA-HBED-CC) is a radiopharmaceutical that will be produced under cGMP at the Cyclotron Radiochemistry of the University of Michigan as described in IND #133858. Inventory recordkeeping requirements, disposition, handling, etc. of the radioactive product is regulated by the NRC. The local regulatory body is the SHUR committee as part of the IRB process.

4.1.2 Furosemide (optional)

Description of furosemide (Trade name: Lasix) Source: [Sanofi-Aventis](#).

A dose of 20 mg of furosemide (Lasix) may be injected i.v. together with, shortly before or after administration of the radiotracer ^{68}Ga -PSMA in order to minimize PET scatter artifacts from excreted radiotracer accumulation in the kidney and urinary bladder. Patients with known adverse effects to furosemide may participate in the study but will not receive Furosemide IV. Potential adverse effects of furosemide include urticaria, rash, and anaphylaxis (rare).

5 Treatment Plan

5.1 Dosage and Administration

The imaging agent (^{68}Ga -PSMA-11) will be administered. It will be administered a single time intravenously prior to the PET imaging. The one-time nominal injected dose will be 3 to 7 mCi of ^{68}Ga -PSMA-11.

5.1.1 Other Modality(ies) or Procedures

5.1.1.1 Change in Management Surveys

Referring clinicians will be required to fill out a pre-imaging survey prior to imaging. Additionally, within 30 days of the completion of imaging, the referring physician will be requested to fill out a post-imaging physician survey, and finally six months (allowed range 3 – 12 months) after imaging, a third physician survey will be filled out.

5.1.1.2 PET Imaging

a) ^{68}Ga -PSMA-11 PET preparation and injection:

The injected dose will be 111-259 MBq (3-7 mCi) of ^{68}Ga -PSMA-11 PET. PET imaging will begin 50-100 minutes after injection (target 75 minutes). Scan time per bed position will be determined based on expected count statistics related to the administered dose.

- b) Patient preparation: no fasting is required. Participants will be asked to void prior to radiotracer injection.
- c) Furosemide administration: A single dose of 20 mg of furosemide (Lasix) may be administered i.v. together with, shortly before or after administration of the radiotracer in order to minimize PET scatter artifacts from excreted radiotracer accumulation in the kidney and urinary bladder. Furosemide should not be administered in subjects with medical contraindications to furosemide administration including allergies and adverse reactions including sulfa allergies.
- d) PET protocol: Scan coverage will extend from mid-thigh to the base of the skull, starting from the mid-thighs to prevent urinary bladder radiotracer accumulation at the start of PET imaging. Additional body parts may be included as deemed necessary based on clinical information, including information from prior diagnostic scans. Scan time per bed position will be determined based on expected count statistics, which is determined mainly by the administered dose. Scan time will therefore be between 15 and 40 minutes.
- e) Patient monitoring: Vital signs will be assessed immediately before and after injection of ⁶⁸Ga-PSMA-11 (HR and supine BP). Patients will be monitored for adverse events during injection and for two hours after radiotracer administration. Additionally, patient's vitals (HR and supine BP) will be checked at the completion of the imaging study prior to leaving the imaging center.
- f) Results dissemination. Scan results will be shared with the subject's clinician and will be reported and stored in the electronic medical record.

5.2 Monitoring and Toxicity Management

Each patient receiving ⁶⁸Ga-PSMA-11 will be evaluable for safety. The safety parameters include physical findings and spontaneous reports of adverse events reported to the investigator by patients.

5.3 Follow-up Standard of Care Imaging

All subjects should be followed as per standard of care consistent with the institution/physician. Reports and copies of any conventional imaging obtained during the 12-month window following the ⁶⁸Ga-PSMA-11 scan will be obtained. Clinical notes will also be reviewed to identify metastatic lesions. Interpretation of follow-up imaging is performed by local institution following standard procedures. Preferable comparison imaging would be the same imaging device as the initial re-staging work-up as per RECIST guidelines. ⁶⁸Ga-PSMA-11 positive findings will be validated as true positive or false positive as outlined in greater detail below.

5.3.1.1 PSMA-positive Lymph Nodes

⁶⁸Ga-PSMA-11 positive nodes will be assessed for change in size using standard of care follow-up imaging.

5.3.1.2 PSMA-positive Osseous or Metastatic Lesions

⁶⁸Ga-PSMA-11 positive osseous or distant metastatic lesions will be followed by other imaging (bone scan, 18F-NaF PET, CT or MRI) at the treating physician's discretion and local standard of care.

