8.3.4 Analysis of Primary Endpoints

Primary endpoint: PPV on a per-patient basis of ⁶⁸Ga-PSMA-11 PET for detection of prostate cancer confirmed by histopathology will be calculated and reported along with the corresponding two-sided 95% confidence intervals. The confidence intervals will be constructed using the Wilson score method.

a) Imaging interpretation ⁶⁸Ga-PSMA-11 PET:

PET images will initially be interpreted by a board certified nuclear medicine physician or a board certified radiologist experienced in reading PET at the time of the imaging study at the University of Michigan. These interpretations will not be used for final evaluation. Upon request, anonymized ⁶⁸Ga-PSMA PET/CT imaging data are sent to the FDA for further review.

Visual interpretation:

Regions of suspected disease will be graded on a two-point scale by each reader (0=Negative or 1= Positive). A region will be judged as positive if at least one lesion in this region is visually positive.

- i) Lymph nodes will be considered positive if the ⁶⁸Ga-PSMA-11 uptake is focal and greater than blood pool (adjacent or mediastinal blood pool). Pelvic lymph nodes will be subclassified according to their localization as follows: R/L obturator, R/L external iliac, R/L internal iliac and other (total of 7 subgroups).
- ii) Visceral lesions will be considered positive if the ⁶⁸Ga-PSMA-11 uptake is focal and greater than physiologic background activity of the involvement organ or anatomic site.

- iii) Bone lesions will be considered positive if the ^{68}Ga -PSMA-11 uptake is focal and greater than physiologic bone marrow.
- iv) Prostate bed and prostate lesions will be considered positive if the ^{68}Ga -PSMA-11 uptake is focal and greater than physiologic background activity of the involvement organ or anatomic site.

b) Follow-up Imaging:

All patients are expected to be followed up as part of clinical care within 3-12 months with conventional imaging (dedicated CT, MRI and/or bone scan). Interpretation of follow-up imaging will be performed by local read. The follow-up conventional imaging should be the same modality/modalities as the initial staging work-up to allow reproducible and accurate comparisons.

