- If on follow-up imaging within 3-12 months, visceral lesions seen on CT or MRI decrease by 30% (for patients undergoing systemic treatment of focal therapy at this site) or increase by 20% in largest diameter.

- If patients with solitary visceral metastasis show a decrease of PSA by greater than 50% after targeted treatment (i.e. external beam radiation) and lesions do not change in size (less than 30% decrease or 20% increase in largest diameter).

(2) False positive:

- If on follow-up imaging within 3-12 months, sites of initial ⁶⁸Ga-PSMA-11 positive lymph node lesions seen on CT or MRI decrease by more than 30% *without* systemic therapy or focal therapy at this site.

- If ⁶⁸Ga-PSMA-11 positive lymph node lesions do not meet the criteria for above false positive or true positive findings.

iii) ⁶⁸Ga-PSMA-11 positive bone lesions will be considered:

(1) True positive:

- If there was a corresponding positive sclerotic lesion on the CT portion of the ⁶⁸Ga-PSMA-11 PET.

- If there is focal uptake seen on the baseline bone scan performed within one month of ⁶⁸Ga-PSMA-11 PET.

- If there is a lesion noted on the initial MRI performed within one month of ⁶⁸Ga-PSMA-11 PET.

- If within 12 months follow-up CT demonstrates development of sclerosis.

- If within 12 months follow-up MRI demonstrates a new bone lesion.

- If within 12 months follow-up bone scan demonstrates new focal uptake.

(2) False positive:

- If ⁶⁸Ga-PSMA-11 positive bone lesions do not meet the criteria for true positive findings.

iv) ⁶⁸Ga-PSMA-11 positive prostate bed and prostate lesions will be considered:

(1) True positive:

- If on follow-up imaging within 12 months, lesions seen on CT or MRI decrease by 30% (for patients undergoing systemic treatment of focal therapy at this site) or increase by 20% in largest diameter.
- If patients with prostate bed lesions show a decrease of PSA by greater than 50% after targeted treatment (i.e. external beam radiation) and lesions do not change in size (less than 30% decrease or 20% increase in largest diameter).

(2) False positive:

- If on follow-up imaging within 3-12 months, sites of initial ⁶⁸Ga-PSMA-11 positive lymph node lesions seen on CT or MRI decrease by more than 30% *without* systemic therapy or focal therapy at this site.
- If ⁶⁸Ga-PSMA-11 positive lymph node lesions do not meet the criteria for above false positive or true positive findings.

c) Histopathology/Biopsy:

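### A PSMA-positive bone lesion whose only confirming evidence is follow-up 18F-NaF PET is scored false positive, because section 5.3.1.2 allows that scan but the bone reference rules in section 8.3.4 b) do not count it

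*Combined protocol and SAP*

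**What the plan says.** Section 5.3.1.2 provides that PSMA-positive "osseous or distant metastatic lesions will be followed by other imaging (bone scan, 18F-NaF PET, CT or MRI"), with the choice left "at the treating physician's discretion and local standard of care". Bone scan and 18F-NaF PET are separate items in that list.

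Section 8.3.4 b) expects all patients to be followed "within 3-12 months with conventional imaging (dedicated CT, MRI and/or bone scan"). NaF PET is not in this list.

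Section 8.3.4 b) iii) gives six ways for a PSMA-positive bone lesion to be a true positive. Three use imaging from around the time of the PSMA scan: "If there was a corresponding positive sclerotic lesion on the CT portion of the" PSMA PET, "If there is focal uptake seen on the baseline bone scan performed within one month of" the PSMA PET, or a lesion on an MRI within the same one-month window. Three use follow-up within 12 months: new sclerosis on CT, a new lesion on MRI, or "If within 12 months follow-up bone scan demonstrates new focal uptake".

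The only bone false-positive rule is residual. It applies when "positive bone lesions do not meet the criteria for true positive findings". There is no indeterminate or not-evaluable class, and section 5.3 likewise foresees only true-positive and false-positive outcomes.

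**The concern.** The section on follow-up and the section on scoring use different lists of scans. A treating physician can follow section 5.3.1.2 exactly, obtain a positive NaF PET, and produce evidence that the scoring rules cannot use. Because the false-positive rule takes everything left over, that lesion is not treated as missing. It is counted as an error of the PSMA scan.

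The endpoints at stake are the PPVs in section 8.3.5, item 1, which use histopathology together with imaging follow-up. Imaging carries most of that composite: section 8.2.1 reports biopsies of PSMA-positive lesions in only 13 of 316 evaluable subjects (13/316 = 4.1%). Bone is one of the four regions in Table 1 for which a PPV will be reported.

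**Working it through.** **Step 1: compare the lists.**

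| Scan | Follow-up allowed (5.3.1.2) | Follow-up list (8.3.4 b) | Bone true-positive criterion (8.3.4 b iii) |
|---|---|---|---|
| CT | yes | yes | yes, PSMA PET/CT and follow-up |
| MRI | yes | yes | yes, baseline and follow-up |
| Bone scan | yes | yes | yes, baseline and follow-up |
| 18F-NaF PET | yes | no | no |

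**Step 2: find which lesions are caught.** A bone lesion is scored false positive because of the mismatch only if all of these hold:
- no matching sclerosis on the CT part of the PSMA scan;
- no qualifying baseline bone scan or MRI;
- no qualifying follow-up CT, MRI or bone scan;
- no positive histology;
- a follow-up NaF PET that would have confirmed it.

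**Step 3: size.** The plan has no figure to reproduce. Let t be the bone PPV if NaF PET counted, and g the share of those true-positive lesions that meet all the conditions in step 2. Both are assumptions. The affected lesions stay in the denominator and leave the numerator, so

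scored PPV = t × (1 - g).

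| t | g = 2% | g = 5% | g = 10% | g = 20% |
|---|---|---|---|---|
| 0.75 | 0.735 | 0.712 | 0.675 | 0.600 |
| 0.90 | 0.882 | 0.855 | 0.810 | 0.720 |

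The direction is always downward.

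**Step 4: why g is smaller than NaF PET use.** Let f be the share of true-positive bone lesions with NaF PET as their only later imaging, and b the share of those that already meet a baseline criterion. Then g = f × (1 - b). With an assumed t = 0.80:

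| b | f = 5% | f = 10% | f = 20% |
|---|---|---|---|
| 0 | 0.76 | 0.72 | 0.64 |
| 0.50 | 0.78 | 0.76 | 0.72 |
| 0.75 | 0.79 | 0.78 | 0.76 |

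For example, b = 0.50 and f = 10% give g = 0.05 and 0.80 × 0.95 = 0.76. The documents give neither f nor b.

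**Step 5: the not-evaluable alternative.** If only the NaF-confirmed lesions are removed from the denominator as well, the PPV is t(1 - g)/(1 - tg). For t = 0.75 this is 0.740 at g = 5% and 0.730 at g = 10%, against 0.712 and 0.675 under the present rule. If the same share of benign lesions also becomes not evaluable, the factor (1 - g) cancels and the PPV stays at t.

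**The case against.** The strongest reply is that section 5.3.1.2 describes what a physician may order, not what counts as proof. Section 5.3 refers to later text for the true- or false-positive rules, section 8.3.4 b) expects every patient to have CT, MRI or bone scan, and section 8.3.5 speaks of conventional imaging. Leaving NaF PET out of the reference could be deliberate. That stands as a possible intention, but it does not justify the score: not accepting a test as a reference is a reason to call the lesion unverified, not to call it a false positive.

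One could also read bone scan as including NaF PET. Section 5.3.1.2 lists them separately, and no section says that one covers the other.

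A further objection is that the residual rule is the wider problem, since it equally catches bone lesions with no follow-up imaging at all. That is right, and it bears on the choice of fix.

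A reader might go further than the documents allow in four ways:
- That any bone lesion with NaF PET as its only later imaging becomes false positive. Three of the six criteria need no later imaging, so many such lesions may already be true positives.
- That the 35% bone share in section 8.2.1 measures the exposure. That figure describes biopsied disease, whereas the lesions at issue are judged by imaging.
- That the pooled analysis will show spurious differences between sites. No section gives NaF PET use by site or plans a comparison between sites.
- That the primary endpoint is compromised. It rests on histopathology; the imaging rules enter only where section 8.3.4 c) sends a bone biopsy with indeterminate pathology back to follow-up imaging.

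**Conclusion.** The inconsistency is real and its direction is certain: read literally, the plan scores as false positive a bone lesion whose only confirmation is follow-up NaF PET. The composite bone-region PPV is biased downward by the factor (1 - g). The composite per-patient PPV is affected less, because a patient with another confirmed lesion should still count as a true positive. The size is unknown and may be small: g is net of every other criterion, and the tables only illustrate assumed values. One case remains open in the text: whether sclerosis on the CT part of a NaF PET/CT would satisfy the follow-up CT criterion. If it does, g is smaller still. The point deserves correction because the repair is short and changes only how lesions are classified.

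**What to change.** Reconcile sections 5.3.1.2, 8.3.4 b) and 8.3.4 b) iii) before the central analysis, in one of two ways.

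1. **Accept NaF PET as a reference.** Extend the follow-up bone-scan criterion so that new focal uptake on either bone scan or 18F-NaF PET qualifies, and add NaF PET to the follow-up list in section 8.3.4 b). Report lesions confirmed by NaF PET alone as a separate count. Leave the baseline bone-scan criterion as it is: section 5.3.1.2 concerns follow-up only and gives no basis for changing it.
2. **Do not accept it.** Classify bone lesions with no qualifying reference imaging or histology, including those followed by NaF PET alone, as not evaluable rather than false positive, and report their number. This also covers lesions with no follow-up imaging, which option 1 alone leaves as false positives.

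The cost is a few words in the analysis rules and a record of the modality used; no patient's imaging or care changes. Under option 1, a few benign lesions may be accepted if NaF PET is less specific than bone scan, and the separate count lets a reader judge this. Under option 2, the PPV denominator is slightly smaller.

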5.3.1.3 Biopsy

Biopsies are performed to determine presence or absence of prostate cancer at the discretion of treating physicians according to standard of care.

5.4 General Concomitant Medication and Supportive Care Guidelines

In general, subjects may receive full concomitant and supportive care throughout this trial.

6 Study Procedures and Observations

See also appendix 2 and 3.

6.1 Schedule of Procedures and Observations

Screening assessments must be performed within 30 days prior to the first dose of investigational product. Any results falling outside of the reference ranges may be repeated at the discretion of the investigator. Treatment or visit delays for public holidays or weather conditions do not constitute a protocol violation.

A written, signed, informed consent form (ICF) and a Health Insurance Portability and Accountability Act (HIPAA) authorization must be obtained before any study-specific assessments are initiated. A copy of the signed ICF will be given to the subject and a copy will be filed in the electronic medical record. The original will be kept on file with the study records.

6.1.1 Screening Assessments

The Screening procedures and assessments must be completed within 30 days of the day 1 Visit.

- Laboratory values: all patients should have a recent PSA (within 30 days prior to study enrollment) consistent with BCR
- Pathology: all patients must have histopathology/biopsy of the prostate with a documented Gleason score
- Performance status: all patients must have their Karnofsky performance status (or ECOG/WHO equivalent) evaluated (Appendix 1).

6.1.2 Treatment Period

6.1.2.1 Study Procedures, Imaging Day 1

- Vital signs
- Evaluation of adverse events

6.1.3 Post-treatment Safety Follow Up

Patients will be followed for acute adverse events for one day (allowed range 1 to 3 calendar days) after the administration of the radiopharmaceutical.

- Evaluation of adverse events

6.2 Prohibited Medications

There are no prohibited medications.

7 Reporting and Documentation of Results

7.1 Evaluation of Efficacy (or Activity)

7.1.1.1 Definitions

Evaluable for toxicity

All patients will be evaluable for toxicity from the time of ⁶⁸Ga-PSMA-11 administration.

7.2 Evaluation of Safety

Analyses will be performed for all patients receiving ⁶⁸Ga-PSMA-11. The study will use the [CTCAE v4.0](#) for reporting of adverse events.

7.3 Definitions of Adverse Events

7.3.1 Adverse Event

An adverse event (also known as an adverse experience) is defined as any untoward medical occurrence associated with the use of a drug in humans, whether or not considered drug related. More specifically, an adverse event (can be any unfavorable and unintended sign (e.g., an abnormal laboratory finding), symptom, or disease temporally associated with the use of a drug, without any judgment about causality. An adverse event can arise from any use of the drug (e.g., off-label use, use in combination with another drug) and from any route of administration, formulation, or dose, including an overdose.

7.3.2 Adverse reaction

An adverse reaction is defined as any adverse event caused by the use of a drug. Adverse reactions are a subset of all suspected adverse reactions for which there is reason to conclude that the drug caused the event.

7.3.2.1 Suspected

A suspected adverse reaction is defined as any adverse event for which there is a reasonable possibility that the drug caused the adverse event. For the purposes of IND safety reporting, “reasonable possibility” indicates that there is evidence to suggest a causal relationship between the drug and the adverse event. A suspected adverse reaction implies a lesser degree of certainty about causality than an adverse reaction.

7.3.2.2 Unexpected

An adverse event or suspected adverse reaction is considered *unexpected* if it is not listed in the investigator brochure or package insert(s), or is not listed at the specificity or severity that has been observed, or, if an investigator brochure is not required or available, is not consistent with the risk information described in the general investigational plan or elsewhere in the current application.

“Unexpected,” as used in this definition, also refers to adverse events or suspected adverse reactions that are mentioned in the investigator brochure as occurring with a class of drugs or as anticipated from the pharmacological properties of the drug, but are not specifically mentioned as occurring with the particular drug under investigation.

Adverse events that would be anticipated to occur as part of the disease process are considered *unexpected* for the purposes of reporting because they would not be listed in the investigator brochure. For example, a certain number of non-acute deaths in a cancer trial would be anticipated as an outcome of the underlying disease, but such deaths would generally not be listed as a suspected adverse reaction in the investigator brochure.

7.3.2.3 Serious

An adverse event or suspected adverse reaction is considered *serious* if, in the view of either the investigator or sponsor, it results in any of the following outcomes:

- Death
- Life-threatening adverse event
- Inpatient hospitalization or prolongation of existing hospitalization
- A persistent or significant incapacity or substantial disruption of the ability to conduct normal life function
- Congenital anomaly/birth defect

Important medical events that may not result in death, are life-threatening, or require hospitalization may be considered serious when, based upon appropriate medical judgment, they may jeopardize the patient or subject and may require medical or surgical intervention to prevent one of the outcomes listed in this definition. Examples of such medical events include allergic bronchospasm requiring intensive treatment in an emergency room or at home, blood dyscrasias or convulsions that do not result in inpatient hospitalization, or the development of drug dependency or drug abuse.

